7.1 General

7.1.1 Design type of clinical investigation

This is a two-arm, double-blind, parallel group, randomized controlled trial (RCT).

The primary endpoint ARSSQ will be assessed once daily. After D8, the ARSSQ will be assessed once daily until the subject feels not sick for two consecutive days.

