7.1.3 Primary Endpoint with methods and timing for assessing recording and analysing variables

The AUC of the global score of the Acute Rhinitis Symptoms Severity Questionnaire (ARSSQ) during first 11 days of symptoms will be compared between both groups.

ARSSQ is a non-validated customized questionnaire (Appendice 1). It includes 10 items assessing symptoms, functional impairments, and global severity. Each item is scored from 0 (not present/no impact/ not sick) to 3 (severe, severe impact and very sick) for symptoms, functional impairment and global severity respectively. Parents/legal guardians will respond to questions according to the evolution of their child's symptoms. This questionnaire is based on the most common symptoms reported for children with common cold and on functional impairments easily evaluable by parents. In order to evaluate the time dependent efficacy of active/placebo, an AUC computation will be carried out.

The ARSSQ assessment will be completed in a paper diary once daily in the evening, taking into account the symptoms from the morning to the evening, within D2-D8 period. After D8, the ARSSQ will be assessed once daily until resolution of all symptoms for 2 consecutive days (question 1 of the questionnaire "not sick" ticked). At D1, the ARSSQ will be completed during the screening/inclusion visit V1. If the patient still has symptoms at V2, ("not sick" not ticked for 2 consecutive days in the previous days), the questionnaire will be also completed during the visit.

To be noticed that the duration may be censored at the end of study participation (visit V2, between day 15 and D18 after inclusion).

- 7.1.4 Secondary Endpoints with methods and timing for assessing, recording and analysing variables
- Comparison of duration of each cold symptom (questions 2 to 7 of the ARSSQ) in both groups.

For each separate symptom, the duration is defined as the number of days between Day 1 and the first day the parent/legal guardian reports the patient not having this symptom ("Not present") for 2 consecutive days.

As mentioned for primary endpoint, duration may be censored at Visit 2.

- Comparison of duration of quality-of-life impairment (questions 8 to 10 of the ARSSQ).

For each separate activity, the duration is defined as the number of days between Day 1 and the first day the parent/legal guardian reports no impact on the patient quality of life ("No impact") for 2 consecutive days.

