The investigator will provide the parents/legal guardians with the device according to the site specific treatment list, in order to respect the 1:1 randomization (blocks of 4). The investigator will explain how to use it.

NB: The first use of the device will be performed in the evening of the Day 1.

D1-D8 up to -D11 (at home):

The Parent/legal guardian will be asked to complete the ARSSQ in the diary, once daily in the evening. The symptoms occurring from the morning to the evening should be taken into consideration. The ARSSQ shall be scored at least from D1 to D8. Adverse events/incidents and concomitant medications are to be reported during the whole period

Between D8 and D11 (at home):

End of Healsea® Babykids/Placebo nasal spray.

➤ NB: The last study nasal spray intake will be performed **between D8 and D11** in the morning. The patient should stop taking the investigational device before D11 only if the question 1 "not sick" of the ARSSQ is ticked YES for 2 consecutive days.

Up to D15/D18 (at home):

Parents/legal guardians will continue to complete the paper diary daily (incidents/adverse events/expected undesirable sides effects, concomitant medications). For patients for whom common cold symptoms persist, parents/ legal guardians will be instructed to continue to complete the ARSSQ, until the subject feels not sick for two consecutive days.

Visit 2 (V2) - (Day 15-Day 18): end of study

The investigator or his/her delegated designee will:

- Perform a physical and clinical examination.
- Collect the patient diary.
- Review the paper diary to validate adverse events pertinent in the context of the common cold, incidents linked to medical device use and concomitant medications reported by the parents/legal guardians. Complete the e-CRF accordingly and report any new relevant safety events
- Ask parents/legal guardians to complete the ARSSQ if the patient still has symptoms.
- Assess the compliance to the treatment by weighing the device bottle returned by the parents/legal guardians. If a nasal spray is not returned or lost, the investigator will ask the

Version 1.1 –2023.02.02 Page **37** of **64**

Study Number: LPH-2202

parents/legal guardians to specify the number of missed nasal spray uses and will report the data into the e-CRF.

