10.2. Analysis of the secondary efficacy criteria

The analysis of the secondary efficacy criteria will involve multivariate analysis.

The selection of variables in multivariate analysis will be performed using a 0.20 significance level and a stepwise method. Covariates considered as potential confounding factors to be initially tested with the treatment in the multivariate models are:

- Body temperature at baseline (°C);
- Scores to each of the items 2 to 7 of the ARSSO at baseline.

All multivariate analyses below will follow this logic.

10.2.1. Modelling of AUC on global score by multivariate ANCOVA

A multivariate ANCOVA model of the AUC on global score of ARSSQ during the first eleven days of the study will be performed.

Patients will be analysed on the FAS and the PP Set.

AXIODIS CRO 17/47

10.2.2. Durations of cold symptoms and of impacts on Quality-of-Life

Hereinafter, the "recovery date" is the first day of the two first consecutive days the patient gave a negative answer to the question 1 ("not sick") without giving a positive answer to the same question (other than "not sick") later. Otherwise, there is no "recovery date" for the patient.

The scores of cold symptoms and of impact on Quality-of-Life (QoL) will be computed at each time-point the patient completed the questionnaire (see §6.4.6), using the following formulae:

At each time point t: ARSSQ_{SYMP}(t) =
$$\sum_{j \text{ in } \{2; ...; 7\}} ARSSQ_{j}(t)$$

ARSSQ_{QOL}(t) = $\sum_{j \text{ in } \{8; ...; 10\}} ARSSQ_{j}(t)$

• The duration of common cold is defined as the duration between the reference start date and the recovery date.

Common cold's duration (days) = Recovery date - Reference start date

The origin date will be the reference start date.

The considered event is the end of common cold, i.e. the recovery of the patient. The event date will be the last day before the recovery date.

Patients without recovery date will be censored at D18 or at the end of the study, and the censoring date will be the date of D18 or the reference end date, whichever occurs first.

• The duration of the cold symptoms is defined as the duration between first symptomatic day and last symptomatic day.

Cold symptom's duration (days) = Last symptomatic day - first symptomatic day + 1

The first symptomatic day is the first day the patient had a non-zero and non-missing score of cold symptoms. It will be the origin date.

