The last symptomatic day is defined as the day before the two first consecutive days the patient had a zero score of cold symptoms without having a non-zero and non-missing score of cold symptoms later. The considered event is the end of cold

AXIODIS CRO 18/47

symptoms, i.e. the definitive nullification of the corresponding score during at least two consecutive days.

The considered symptomatic days are between D1 and either D18, or the end of the study, or the day before the recovery date, whichever occurs first. Symptomatic days from the recovery date will not be taken into account.

For patients who definitely nullified the score of cold symptoms, or for patients with a recovery date, the event date will be the last day before the definitive nullification of the score of cold symptoms, or before the recovery date if it exists.

Patients who did not definitely nullify the score of cold symptoms, and without recovery date, will be censored at D18 or at the end of the study, and the censoring date will be the date of D18 or the reference end date, whichever occurs first.

For patients who never had a non-zero score of cold symptoms (never ticked "mild", "moderate" or "severe" for any symptom) and having completed the questionnaire at D1, the origin date for the symptom will be D1, the cold symptoms will be censored at D1 and the duration will be zero. If patients who never reported the presence of any symptom did not complete the questionnaire at D1, neither origin date nor censoring date will be defined for cold symptoms and the duration will be missing.

• The duration of impact on QoL is defined as the duration between first impacted day and last impacted day.

Impact on QoL's duration (days) = Last impacted day – first impacted day + 1

The first impacted day is the first day the patient had a non-zero and non-missing score of impact on QoL. It will be the origin date.

The considered event is the end of impact on QoL, i.e. the definitive nullification of the corresponding score during at least two consecutive days. The last impacted day is defined as the day before this definitive nullification, and the duration is computed by the same way as for cold symptoms' duration.

A Cox survival regression model will be used to analyse each of the durations of common cold, of cold symptoms and of impact on QoL.

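### SAP 10.2.2 lets a later positive answer void or delay recovery, but the diary schedule exposes only early recoverers to that condition

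*SAP*

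**What the plan says.** **Recovery date (SAP 10.2.2).** It is the first of the two first consecutive days answered 'not sick' on question 1, but only "without giving a positive answer to the same question (other than 'not sick') later". If that fails, "Otherwise, there is no 'recovery date' for the patient", and "Patients without recovery date will be censored at D18 or at the end of the study", whichever comes first.

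**Symptom and quality-of-life ends (SAP 10.2.2).** The cold-symptom score must be zero on two consecutive days "without having a non-zero and non-missing score of cold symptoms later". The quality-of-life duration is computed in the same way. Symptomatic days from the recovery date onward are ignored, and a recovery date itself supplies an event.

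**Diary schedule.** Protocol 7.4.1: "The ARSSQ shall be scored at least from D1 to D8". Protocol 7.1.1: "After D8, the ARSSQ will be assessed once daily until the subject feels not sick for two consecutive days". Protocol 7.1.3 repeats the stopping rule and asks for a questionnaire at V2 only from children without such a pair.

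**Other definitions.** Protocol 7.1.4 ends each symptom at "the first day the parent/legal guardian reports the patient not having this symptom" for two consecutive days, and treats questions 8 to 10 likewise, with no look-ahead. SAP 7.2, on minor deviations, describes recovery as two consecutive 'not sick' answers and nothing more. SAP section 12 reports that question 1 now helps to close the symptom and quality-of-life durations. It does not list the 'no later positive' condition as a change from the protocol.

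**The concern.** A sustained-recovery endpoint is fair only if every child is observed for the same time after recovering. Here the time left depends on when the child recovers, because the diary is compulsory to a fixed day and then closes at the first 'not sick' pair. Early recoverers face several more scheduled questions, and one stray positive can cost them their date. Children who recover from D7 face none.

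If the device speeds recovery, more treated than placebo children recover early and are exposed to the condition. A real benefit would then look smaller in the three Cox models, the forest plots, and the Kaplan-Meier curves with their log-rank p-values.

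The sentence is also ambiguous about a child who relapses once and recovers again, so two programmers could code different events from it.

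**Working it through.** **Plan's own figure.** The plan states none for the durations. Its sample size (100 per arm, d = 0.4, 80% power, two-sided 5%) concerns the AUC only and reproduces: 2 × (1.960 + 0.842)² / 0.4² = 98.1, so 99 per arm.

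**Step 1: scheduled look-ahead.** A first pair starting on day k occupies days k and k + 1. The compulsory diary runs to D8, which leaves 8 − (k + 1) = 7 − k answers. From k = 7 the diary closes as the pair completes. With an assumed daily relapse risk r, the chance of at least one later positive is 1 − (1 − r)^(7−k).

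| First 'not sick' day k | Answers left | r = 2% | r = 5% | r = 10% |
|---|---|---|---|---|
| D2 | 5 | 9.6% | 22.6% | 41.0% |
| D3 | 4 | 7.8% | 18.5% | 34.4% |
| D4 | 3 | 5.9% | 14.3% | 27.1% |
| D5 | 2 | 4.0% | 9.8% | 19.0% |
| D6 | 1 | 2.0% | 5.0% | 10.0% |
| D7 or later | 0 | 0% | 0% | 0% |

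The column of answers left follows from the documents. The percentages depend on r, which the documents do not give.

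**Step 2: two children** (duration = recovery date − D1).
- Child A is sick D1–D4, not sick D5–D6, a little sick D7, not sick D8–D9. The first pair gives 5 − 1 = 4 days. The pair after the last positive gives 8 − 1 = 7 days. Read literally, the first pair fails, there is no recovery date, and the child is censored at D18 or end of study.
- Child B is sick D1–D6 and not sick D7–D8, when the diary closes. A relapse on D9 has no scheduled entry. The result is 7 − 1 = 6 days under every rule.

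Child A was first well two days before Child B but is scored as longer, or as unrecovered.

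**Step 3: effect on the hazard ratio.** None of these inputs is in the documents: 20,000 simulated children per arm; Weibull time to the first 'not sick' day, with a placebo median of D6 or D8; relapse risk of 2%, 5% or 10% per well day after the first pair; relapses of 1–3 days; true hazard ratio 1.0 or 1.5. The diary closes at D8 if D7 and D8 are both 'not sick', otherwise at the first later pair. Cox models use Efron ties. Hazard ratios for r = 2% / 5% / 10% and true value 1.5:

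| Rule | Median D6 | Median D8 |
|---|---|---|
| First pair, no look-ahead | 1.48 / 1.50 / 1.49 | 1.48 / 1.50 / 1.50 |
| Pair after the last positive | 1.45 / 1.39 / 1.36 | 1.48 / 1.49 / 1.48 |
| Literal: void and censor | 1.33 / 1.22 / 1.15 | 1.40 / 1.31 / 1.23 |

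At median D6 the literal rule removes the date from 2.8 / 7.2 / 13.1 children per 100 in the faster arm and 2.2 / 5.1 / 10.4 in the slower arm. No child first well from D7 loses it. With a true hazard ratio of 1.0, all three rules give 0.99–1.01.

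The loss under the middle rule is sensitive to the relapse model. It is 0.03–0.13 at D6 here. A separate run with 8,000 per arm and a 3–10% daily chance of a stray positive gave 0.06 or less at D6–D8.

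**The case against.** **Sustained recovery is a legitimate endpoint.** Protocol section 4 counts recurrence after initial improvement among the criteria for bacterial rhinosinusitis, so relapse matters in this disease. This stands. It is a reason to report relapse and keep a sensitivity analysis, but it does not make the look-ahead equal.

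**A reader might infer that relapsed early recoverers are certainly censored as never recovered.** The documents do not settle that. The sentence can also mean the first pair that no positive follows. For symptoms, SAP 10.2.2 speaks of definitive nullification, and section 12 ends a symptom at the last symptomatic day followed by two absences. On that reading recovery is only delayed.

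**A reader might infer that late recoverers can never lose their date.** That is true of scheduled entries only. Parents may record unasked, and Protocol 7.4.1 has the questionnaire completed at V2 if symptoms persist, which is looser than 7.1.3.

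**A reader might carry the D7 cut-off over to symptoms and quality of life.** It does not transfer. Days from the question 1 recovery date are ignored, and a child free of symptoms but still sick keeps the diary open. The effect there is partial, and the simulation covers recovery dates only.

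**A reader might infer that the protocol has a question 1 duration rule to restore.** It has none. Its durations cover questions 2 to 10, and the duration of common cold is the SAP's own endpoint.

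**Size and status.** SAP 6.3.1 makes all secondary results descriptive, and the primary AUC is untouched. Assuming 190 events, SE(log HR) = √(4/190) = 0.145. The largest delayed-recovery loss, ln(1.49/1.36) = 0.091, is about 0.6 SE. The largest literal loss, ln(1.49/1.15) = 0.259, is about 1.8 SE. The first is modest; the second is not.

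**Conclusion.** The concern holds in a limited form. The unequal look-ahead follows directly from the diary schedule and the SAP's condition. The condition departs from the protocol's durations for questions 2 to 10 and is not declared in section 12. Its direction is to weaken a true benefit; under equal arms it produces no bias, so this mechanism does not create a false one.

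The size depends on which reading is programmed and on relapse rates that the documents do not give. Under the assumptions above, a true 1.5 becomes about 1.15–1.40 on the literal reading and about 1.36–1.49 if recovery is only delayed.

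One uncertainty remains. The stopping rule does not say whether a pair completed before D8 already satisfies it. If it does, a child in relapse on D8 may stop the diary there and be censored under either reading.

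The change is worth making because a stated secondary objective rests on these durations and the correction is cheap.

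**What to change.** In SAP 10.2.2:
- For the main Cox and Kaplan-Meier analyses, end the symptom and quality-of-life durations at the first of the first two consecutive negative days, as in Protocol 7.1.4.
- Apply the same two-day rule to the SAP's duration of common cold, which matches the diary-stop rule and SAP 7.2.
- Report recorded relapse after that date by arm, descriptively, noting that scheduled observation is unequal.
- Keep definitive recovery only as a sensitivity analysis, worded as the first pair of consecutive negative days after the last positive answer, so that a child who recovers again has an event.
- Reconcile SAP 7.2, 10.2.2 and 12, and list the change in section 12.

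A longer diary would not rescue the literal rule. With complete diaries to D18, the same simulation gives 1.15 / 1.02 / 0.96 at median D6 and 1.16 / 1.05 / 0.93 at D8, because early recoverers still have the longer look-ahead.

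The cost is wording and a few lines of code, with no new data. The small downside is that a short remission counts as recovery in the main analysis.

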^{*} Treatment dispensation

^{**} ARSSQ to be completed with the investigator on site at screening and at the end of the study if the patient still has symptoms ("not sick" not ticked for 2 consecutive days in the previous days). After day 8, until complete resolution of symptoms for 2 consecutive days (question 1 of the questionnaire).
Treatment from D1 to D8 and up to D11.

^{***} Medical History - Relevant medical history in connection to infectious acute rhinitis, allergic rhinitis, nasal disorders and asthma back to 2 years

3. Identification and description of the investigational device and of the Placebo

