5.6 Rational for the benefit risk ratio

Although infectious rhinitis is in most cases self-limiting, it impacts the children's quality of life during generally about 7 to 10 days. Furthermore, bacterial over-infections with worsening of symptoms can occur requiring antibiotic prescription. Progression to a chronic state, i.e. chronic rhinosinusitis is also observed.

Conventional therapies for infectious rhinitis are symptomatic and are not without side effect. For example, decongestant use can increase blood pressure, antihistamine intake is associated with drowsiness.

Healsea® Babykids represents an interesting alternative because this nasal spray could alleviate infectious rhinitis symptoms but also limit the complication and progression to chronic state.

Furthermore, there is no expected side effect.

6. Objectives and hypotheses of the clinical investigation

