6.4.6. Scores of ARSSQ

To compute any score of ARSSQ, if the questionnaire has been completed at a given time point except some items, these missing answers will be imputed by the last observation carried forward (LOCF).

At time points the questionnaire has not been completed at all, no imputation will be done and the score will be missing.

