12. CHANGES IN THE CONDUCT OF THE STUDY OR PLANNED ANALYSIS

The planned analysis in the protocol to assess the primary objective (multivariate ANCOVA model of the AUC on global score of ARSSQ during the first eleven days of the study) has been replaced by the comparison of the means of the AUC on global score of ARSSQ during the first eleven days of the study between treatment groups. The multivariate ANCOVA has been put among secondary analyses.

This change has no impact on the relevance of the sample size calculation since the primary endpoint is the same as planned in the protocol.

Moreover, since several patients still reported having symptoms while they reported they did not feel sick anymore at the question 1 during at least the two last days of completion of the ARSSQ, their positive answers to the cold symptoms' items have been considered as non-significant. Consequently, the question 1 has been taken into account in addition to the corresponding items to determine the end of the cold symptoms' duration, however only on the condition that the last days of completion were consecutive.

If the last days of completion were not consecutive, positive answers to cold symptoms' items are still considered as symptomatic, even if the two last answers to the question 1 are negative. The symptom ends at the last symptomatic day if the patient reported the absence of this symptom at least twice and consecutively after this day. Otherwise, the duration of the symptom is censored at D18 or at the end of the study, whichever occurs first.

The same change has been applied to compute the duration of impact on QoL.

AXIODIS CRO 25/47

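### Secondary durations (minor): a recovery split by a missed diary day can be carried as unrecovered to D15–D18, and the QoL clock starts at first impairment instead of Day 1, a change SAP 12 does not list

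*SAP*

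**What the plan says.** **Recovery and censoring.** SAP 10.2.2 dates recovery at the first of two consecutive days answered as not sick on question 1, with no later positive answer. Without such a pair there is no recovery date, and "Patients without recovery date will be censored at D18 or at the end of the study", whichever comes first. The cold-symptom duration follows the same pattern with a zero score, or ends at the recovery date if there is one. On wholly missed days SAP 6.4.6 states: "At time points the questionnaire has not been completed at all, no imputation will be done and the score will be missing".

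**Diary instruction.** Protocol 7.4.1 asks parents of children with persisting symptoms to continue the ARSSQ "until the subject feels not sick for two consecutive days". Protocol 7.1.3 adds an ARSSQ at Visit 2 when no such pair exists.

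**QoL duration.** Protocol 7.1.4 counts from Day 1, separately for each activity, to the first day of two consecutive no-impact days. SAP 10.2.2 uses the sum of items 8 to 10 and another origin: "The first impacted day is the first day the patient had a non-zero and non-missing score of impact on QoL". The end is the definitive return of that score to zero. The remainder is computed as for cold symptoms, where a child who never scores above zero and completed D1 is censored at D1 with duration zero.

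**Status.** SAP 6.3.1 treats all secondary results as descriptive, with p-values for information only.

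**The concern.** Two groups of children with good outcomes may not count as such.

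(a) A child can be well, and recorded as well on two diary days, yet be carried as unrecovered to the end of the study because the day between was missed. The censoring date is tied to D18 or study end, not to the last day on which anything was recorded.

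(b) A child never impaired on QoL has the best possible outcome on that measure. If censored at time zero, this child contributes nothing to the Cox or log-rank comparison, so a device that prevented impairment could not show it in the hazard ratio. The SAP origin can also fall after randomisation, unlike the protocol's Day 1.

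The results will appear as hazard ratios, forest plots and log-rank p-values, each with a stated favourable direction (SAP 10.2.2), so what they measure should be clear.

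**Working it through.** The documents give no event count, power or missed-day rate for these durations, so there is no planned figure to reproduce on this point. The 100 per arm belongs to the primary test: 2 × (1.960 + 0.842)² / 0.4² = 98.1, so 99 per arm. It is used below only as the sample size.

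**Step 1. The recovery rule on example diaries** (sick through D8; duration = recovery date − start date):

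| Diary after D8 | Recovery date | Duration |
|---|---|---|
| D9, D10 not sick | D9 | 9 − 1 = 8 |
| D9 not sick, D10 missed, D11 not sick, diary stops | none | censored D15–D18 |
| the same, plus one not-sick answer at V2 on D16 | none | censored D15–D18 |
| D9 not sick, D10 missed, D11 and D12 not sick | D11 | 11 − 1 = 10 |

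A gap mostly delays the date by a day or two if the diary is kept as instructed. It removes the event if the diary stops early.

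**Step 2. Size of the gap effect.** Assumptions, none from the documents: true hazard ratio 1.35, Weibull recovery times (shape 2.5), placebo median 8 days, days missed at random and equally in both arms. The median is guided by Protocol 5.6, which says colds affect "quality of life during generally about 7 to 10 days". V2 is on D15–D18 and its ARSSQ is done whenever no consecutive pair exists. There were 1,000 runs per row, Cox with Efron ties.

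| Diary behaviour | Missed days | Complete data | SAP rule | Wrongly held unrecovered |
|---|---|---|---|---|
| As instructed | 5% | 1.349 | 1.345 | 0.3% |
| As instructed | 10% | 1.349 | 1.337 | 1.0% |
| Stops after two gap-split entries | 5% | 1.349 | 1.283 | 4% |
| Stops after two gap-split entries | 10% | 1.349 | 1.243 | 8% |

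In the last row, placebo medians of 7 and 10 days give 1.22 and 1.28. A separate simulation of 300 runs per row gave 1.32 and 1.31 as instructed (0.2% and 0.6% held), and 1.28 and 1.23 with early stopping (3.8% and 7.8% held).

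**Step 3. Censoring at the last ARSSQ.** If 10% of diaries per arm end at random between D4 and D12 and there is no V2 ARSSQ, the SAP rule gives 1.284, last-ARSSQ censoring 1.366 and complete data 1.364. With the V2 ARSSQ done, both rules give 1.284.

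**Step 4. Weight of children censored at time zero.** The Cox partial likelihood is the product over events i of exp(βx_i) / Σ exp(βx_j), summed over children with t_j ≥ t_i. Impaired children have durations of at least 1 day (last − first + 1), so a child censored at 0 is in no risk set. As a check, 20 such children (5 placebo, 15 active) were added to an artificial data set of 200. The hazard ratio (0.9624), standard error (0.1457) and log partial likelihood (−845.695) were unchanged.

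**Step 5. Size of the QoL effect.** The D1 ARSSQ is completed at V1 (Protocol 7.1.3) and the first spray follows that evening (Protocol 7.4.1). Prevention can therefore act only on children unimpaired at D1, a share that randomisation balances. Assumed shares, with onset at D2–D4 if not prevented:

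| Unimpaired at D1, both arms | Staying so, active v placebo | Never impaired | HR from Day 1 | HR, SAP |
|---|---|---|---|---|
| 5% | 75% v 50% | 3.75% v 2.5% | 1.02 | about 1.00 |
| 10% | 75% v 50% | 7.5% v 5% | 1.04 | about 1.00 |
| 15% (extreme) | 100% v 33% | 15% v 5% | 1.18 | about 1.00 |

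**Step 6. Disclosure.** SAP 12 lists the new primary test and the use of question 1 in ending the symptom and QoL durations. It mentions neither the change of origin nor the move from separate activities to a summed score.

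**The case against.** The two-consecutive-day rule and censoring at Visit 2 are the protocol's own, and the V2 ARSSQ is meant to catch children without a pair. This stands, and it is why part (a) is negligible when the diary is kept as instructed. It does not remove the case: one not-sick answer at V2 forms no pair, and the censoring date ignores the last entry.

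SAP 12 shows that gaps were foreseen. It uses question 1 "only on the condition that the last days of completion were consecutive", and otherwise ends a symptom "if the patient reported the absence of this symptom at least twice and consecutively after this day". A reader might infer that this leaves open whether days or reports are meant. SAP 10.2.2 speaks of days throughout, so calendar days is the natural reading. The sentence concerns children still reporting symptoms and does not rescue gap-only children.

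The D1 censoring is written for cold symptoms and reaches QoL only by cross-reference. The same section also makes patients with a recovery date events, so the zero weight is the apparent rule, not a settled one. Never-impaired children may also be few: entry requires at least moderate nasal congestion, and breathing is a QoL item.

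Two stronger readings are not supported:

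- A reader might infer that unequal gaps could reverse the treatment effect. The trial is blinded and the documents give no reason for imbalance.
- A reader might infer a sizeable hidden QoL benefit from assuming 15% v 5% never impaired with onset at D1 in all others (1.12 from Day 1 against 1.00). Those arms already differ before the first spray, so 1.12 is baseline imbalance, not prevention.

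Finally, the simulations assume no relapse and random gaps, which favours a gap-tolerant rule. They do not show that it is better for fluctuating colds, where two consecutive days give protection.

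**Conclusion.** The point holds and is minor. It concerns secondary, descriptive results; the primary AUC comparison and the sample size are unaffected.

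For (a), the text allows a recovered child to be analysed as unrecovered to D15–D18. At an assumed 5% to 10% of days missed, this affects about 1% of children or fewer with instructed diaries. It affects 4% to 8% if parents stop early, which pulls the hazard ratio toward 1.

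For (b), the change of origin and its absence from SAP 12 are facts of the text and need no assumed rate. The SAP must also say which rule governs never-impaired children. If they are censored at time zero, the hazard ratio cannot reflect prevention. The likely loss is small, and would be larger only if many children are unimpaired at D1, a share the documents do not give.

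**What to change.** 1. Analyse QoL duration from Day 1, as in the protocol, with never-impaired children counted as resolved at the shortest duration. Keep the SAP version as a sensitivity analysis and state there whether the never-impaired rule or the recovery-date rule prevails. List in SAP 12 the changes of origin, of end rule (first two consecutive no-impact days against definitive zero) and from separate activities to a summed score. The end rule must be explicit, because a child unimpaired on D1 and D2 but impaired later is treated differently under the two.
2. Censor children without a recovery date at the last completed ARSSQ, including V2. This changes nothing when the V2 ARSSQ was done.
3. As a sensitivity analysis to the two-consecutive-day rule, count as recovered any child whose not-sick (or zero-score) entries are separated only by missing days with no later positive answer. Use interval censoring or the midpoint between the last sick and first not-sick entry. Report the number of such children by arm.

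The cost is a few lines of SAP text and derivation code on data already collected, and slightly earlier censoring for some children. Counting QoL from Day 1 combines prevention with duration, which is why the SAP version stays as a sensitivity analysis.
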